#### Table 8: Sample Size 2-stage Group Sequential Design

## 7.2 DERIVATION OF PERFORMANCE GOAL

The primary safety endpoint performance goal was derived from the following 22 studies, summarized in **Table 9**.

Table 9: Safety	Performance	Goal Literature	Summary
-----------------	-------------	------------------------	---------

First Author	Subjects	In-Hospital ACM	Bailout to Alternative Thrombus Removal Strategy	Clinical Deterioration (within 24 hours)	Major Bleeding (BARC3b/3c/5a/5b)
Avgerinos et al. 2017	90	15/90, 16.6%	NS	NS	24/90, 26.6%
Barrett et al. 2010	SE: 9	6/9, 66.6%	NS	NS	NS
	TL: 10	6/10, 60.0%			
	AC: 14	5/14, 35.7%			
Carvalho et al. 2010	16	7/16, 43.8%	NS	NS	NS
Cho et al. 2016	19	NS	4/19, 21.0%	NS	NS
	26		NS		
Corsi et al. 2017	17	NS	NS	NS	NS
de Winter et al. 2019	33	NS	8/33, 24.2%	NS	NS
George et al. 2018	32	15/32, 46.9%	NS	5/32, 15.6%	NS

First Author	Subjects	In-Hospital ACM	Bailout to Alternative Thrombus Removal Strategy	Clinical Deterioration (within 24 hours)	Major Bleeding (BARC3b/3c/5a/5b)
Hartman et al. 2015	24	NS	NS	NS	NS
Kuo et al. 2015	28	4/28, 14.3%	NS	NS	0/28, 0.0%
Minakawa et al. 2018	63	23/63, 36.5%*	NS	NS	NS
Moon et al. 2018	Without ECMO: 9	7/9, 77.8%	NS	NS	NS
	ECMO:14	8/14, 57.1%			7/14, 50.0%
Munakata et al. 2012	10	3/10, 30.0%†	NS	NS	2/10, 20.0%
Neely et al. 2015	49	5/49, 10.2%*	NS	NS	1/49, 2.0%
Niwa et al. 2012	289	NS	NS	NS	NS
Desriis et al. 2010	Control: 27	5/27, 18.5%	NS	NS	3/27, 11.1%
Pasrija et al. 2018	Protocol: 29	1/29, 3.4%			4/29, 13.8%
Roncon et al. 2018	47	NS	NS	NS	NS
	30				
Secemsky et al. 2019	46	15/46, 32.6%	NS	NS	11/46, 23.9%
Senturk et al. 2016	186	NS	NS	NS	10/186, 5.4%
Sharifi et al. 2016	23	2/23, 8.7%	NS	NS	0/23, 0.0%
Shiomi et al. 2017	31	4/31, 12.9%	NS	NS	NS
Ucar et al. 2013	107	18/107, 16.8%	NS	NS	4/107, 3.7%
Wang et al. 2010	20	NS	12/20, 60.0%	NS	NS
	20		4/20, 20.0%		
Total	1,318	149/607	28/92	5/32	66/609
Weighted Average [95% Confidence Intervals]	NA	28.5% [20.6%, 37.9%]	30.3% [15.5%, 50.7%]	15.6% [6.7%, 32.5%]	11.5% [6.0%, 21.0%]

AC, Anticoagulation; ACM, All-Cause Mortality; BARC, Bleeding Academic Research Consortium; ECMO, Extracorporea Membrane Oxygenation; NA, Not Applicable; NS, Not Specified; SE, Surgical Embolectomy; TL, Thrombolytic Therapy \*Operative mortality was reported. Only patients in refractory shock were included in the analysis. †All patients died within 15 hours of the procedure.

The Performance Goal is a weighted average calculated from each individual component of the composite endpoint; each component is a result of a meta-analysis across previous publications using the random-effects model. The Performance Goal weighted average is 21.5%, and by using a 10% margin with rounding up to the nearest percent, the Performance Goal for the study is 32%.

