## 6.1.2 Patient Flow and Schedule of Assessments

Patient enrollment by study Arm study is provided in the Figure 4 flowchart. The Schedule of Assessments is included in Table 3.

Table 3:	Schedule of Assessments
----------	-------------------------

Assessment	Baseline	Procedure	Post-procedure through Hospital Discharge
Eligibility 	Х		
Medical History 	Х		
Pre-procedure presentation and status 	Х		
Anticoagulation 	Х	Х	Х
Thrombolytic Therapy 	Х	Х	Х
Primary Treatment Plan Decision for high-risk PE 	Х		
Primary Treatment Initiated for high-risk PE 		Х	
Bailout therapies for high-risk PE 		Х	Х
Clinical Deterioration 		Х	Х
Major Bleeding Events 		Х	Х
Adverse Events 		X	X
Discharge details			Х

Data used to determine eligibility include pre-treatment data only.

Data collected for subject Medical History include pre-treatment data only.

Signs and symptoms of high-risk PE beginning should be reviewed for eligibility. Data should also be collected for subjects first presenting with low/intermediate-risk PE who progress to high-risk PE in the same hospital setting/admission, including any treatment given to treat the low/intermediate-risk PE.

Anticoagulation and thrombolytic therapy administration are not required, but if administered, detailed data will be

collected including drug name, dosage, start and stop dates/times, route, and reason for administration.

The Primary Treatment plan for treating the high-risk PE will be documented including the date and time that the Primary Treatment plan was decided.

The date and time the Primary Treatment for thrombus removal is initiated will be documented. The patient is considered enrolled at the time the Primary Treatment for high-risk PE is initiated (the time of enrollment for patients in the Prior Therapy Arm will be the time of high-risk PE diagnosis).

Any bailout therapies for thrombus removal applied after initiation of the Primary Treatment therapy through hospital discharge will be documented and subsequently adjudicated by the CEC. See Section 6.1.4.1 for details.

Clinical deterioration occurring after initiation of the Primary Treatment therapy through hospital discharge will be documented and subsequently adjudicated by the CEC. See Section 6.1.4.2 for details.

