## 6.1.4.2 Clinical Deterioration

Subject clinical status will be monitored and recorded in the study records. Signs of clinical deterioration observed from the time of initiation of the Primary Treatment for high-risk PE through hospital discharge will be recorded by the site and adjudicated by the Clinical Events Committee (CEC, **Section 6.3**), and is defined in **Table 5** below.

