## 6.1.6 Study Exit

Subjects may be exited from the study if they are deceased prior to discharge. As this study is only looking at outcomes through hospital discharge, it is not expected that subjects will be lost to follow-up. Subjects who remain in-hospital (from the index hospitalization for high-risk PE) for  $\geq$  45 days after the Primary Treatment for high-risk PE will be exited from the study at that time, as the study is considering acute outcomes for the treatment of high-risk pulmonary embolism.

Study Exit for all subjects, regardless of reason, will be documented on a Study Exit form in the study record.

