## 6.3 CLINICAL EVENTS COMMITTEE (CEC)

A Clinical Events Committed (CEC) will be utilized in this study for the purposes of adjudicating the primary and secondary endpoints. Site-reported safety and outcome data will be provided to the CEC for review and adjudication of the following items for all FlowTriever and Context Arm subjects enrolled in the study:

- Classification as a Serious Adverse Event (SAE)
- Determination of relatedness
- Assessment of severity
- Assessment of endpoint criteria

Adjudication will be conducted according to the FLAME CEC Charter.

(Note that the primary endpoint will only be analyzed for subjects in the FlowTriever Arm of the study, but the CEC will adjudicate events for subjects enrolled in the Context Arm of the study as well)

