# 7 STATISTICS & DATA ANALYSIS

## 7.1 SAMPLE SIZE

The sample size of the FlowTriever Arm is calculated using a two-stage group sequential design, where the FlowTriever Arm is expected to have a rate of in-hospital composite endpoint of all-cause mortality, bailout to an alternative thrombus removal strategy, clinical deterioration, and major bleeding (BARC 3b/3c/5a/5b definition) of 18%. The rate of the FlowTriever Arm composite endpoint is compared with the historical performance goal of 32%, based on meta-analysis results shown in Table 9. A one-sided binomial proportion's test with normal approximation is used against the historical performance goal with a power of 80% and a one-sided  $\alpha = 0.05$ ; O'Brien Fleming boundary was implemented where the first stage, or interim analysis, is planned at N = 50 subjects enrolled and consequently arriving at the second stage, or final analysis, with N = 71 subjects as shown in Table 8.

Analysis Stage	N	Z-score Threshold	P-value Threshold	FT Event proportion	Significant event number
Interim	50	-2.0311	0.0211	0.186	≤9.3
Final	71	-1.7116	0.0435	0.225	≤16.0

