## 7.4 ENDPOINT ANALYSIS

## 7.4.1 PRIMARY ENDPOINT ANALYSIS

The primary endpoint is the in-hospital composite endpoint of all-cause mortality, bailout to an alternative thrombus removal strategy, clinical deterioration, and major bleeding (BARC 3b/3c/5a/5b definition) from the FlowTriever Arm. The rate of the composite endpoint is expected to be 18% and compared with performance goal of 32%:

H0:  $P_S \ge Performance Goal_s versus H_A: P_S < Performance Goal_s$ 

where Ps is the proportion of subjects with in-hospital composite endpoint and Performance Goals is the performance goal of proportion of subjects with in-hospital composite endpoint derived from previous publications and expert opinions on subjects who were non-FlowTriever treatments.

The one-sided binomial's proportion test with normal approximation would be used at a one-sided  $\alpha$  = 0.05. Primary endpoint analysis can be carried out at interim analysis and/or final analysis stage.

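### Does the 24-hour deterioration rate behind the 32% performance goal need to be matched to the trial's through-discharge window?

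*Protocol*

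**What the plan says.** Protocol 7.2 and SAP 5.2 build the goal from four literature components. The deterioration column is headed "Clinical Deterioration (within 24 hours" in both documents. Its only entry is one study with 5/32 = 15.6% (95% CI 6.7% to 32.5%). The average of the components is given as 21.5%, and the goal becomes 32% "by using a 10% margin with rounding up to the nearest percent".

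The trial's own window is longer. Table 3 in Protocol 6.1.2 says: "Clinical deterioration occurring after initiation of the Primary Treatment therapy through hospital discharge will be documented and subsequently adjudicated by the CEC". Section 6.1.4.2 agrees: "Signs of clinical deterioration observed from the time of initiation of the Primary Treatment for high-risk PE through hospital discharge will be recorded". Under 6.1.6, a subject still in hospital at 45 days "will be exited from the study at that time, as the study is considering acute outcomes".

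The test is on the in-hospital composite. Protocol 7.4.1 says: "The rate of the composite endpoint is expected to be 18% and compared with performance goal of 32". Protocol 7.1 and SAP 5.1 use the same 18% and 32% for the sample size. The rate of each component is a secondary endpoint (Protocol 7.4.2, SAP 5.4), and the Context Arm is described with the same endpoints (SAP 2 and 2.3).

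**The concern.** A benchmark and the endpoint tested against it should cover the same period. Here one of the four terms stops at 24 hours, while the trial keeps counting for the whole stay. The mortality column is headed as in-hospital; deterioration is the only column whose heading gives a window shorter than the endpoint's. The documents neither adjust for this nor mention it.

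A benchmark that is too low makes the goal too strict. If the trial missed narrowly, a reader could not tell a real shortfall from late deterioration that the benchmark never observed. Whole events decide the result: 16 events in 71 give z = -1.7097 against a threshold of -1.7116, so one subject can matter.

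**Working it through.** **Inputs.** Component rates from Protocol Table 9: mortality 28.5%, bailout 30.3%, deterioration 15.6%, major bleeding 11.5%. Thresholds from Table 8: z = -2.0311 at N = 50 and z = -1.7116 at N = 71.

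**Reproducing the goal.** (28.5 + 30.3 + 15.6 + 11.5)/4 = 85.9/4 = 21.475, printed as 21.5%. Adding 10 gives 31.475, rounded up to 32%. The plan calls this a weighted average. Equal weights are inferred because they reproduce the figure; weighting by subjects gives 20.6%. Deterioration then has one-quarter weight and contributes 15.6/4 = 3.9 of the 21.475 points.

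**Direction.** Everyone who deteriorates within 24 hours has also deteriorated by discharge. With the definition and time zero held fixed, the matched rate x is at least 15.6%, so a matched goal is at least 32%.

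**Size.** Goal = (28.5 + 30.3 + x + 11.5)/4 + 10, rounded up. Event limit = n(g - |z|√(g(1-g)/n)), where g is the goal as a proportion. The documents give no through-discharge value, so every row after the first is an assumption.

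| x | Before rounding | Goal | Limit, N = 50 | Limit, N = 71 |
|---|---|---|---|---|
| 15.6% (plan) | 31.475 | 32% | 9.30 | 15.99 |
| 17.7% | 32.000 | 32% | 9.30 | 15.99 |
| 18.75% (6/32) | 32.2625 | 33% | 9.75 | 16.65 |
| 20% | 32.575 | 33% | 9.75 | 16.65 |
| 25% | 33.825 | 34% | 10.20 | 17.31 |
| 30% | 35.075 | 36% | 11.11 | 18.64 |

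The first two rows reproduce Table 8 (9.3 and 16.0). In whole events, the limit at N = 71 would be 16, 17 or 18 for goals of 33%, 34% or 36%. The current limit is 15 if the unrounded 15.99 is applied, or 16 as Table 8 prints it.

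**Effect on false success.** With limits of 9 at N = 50 and 16 at N = 71, the exact probability of passing at true rate p is P(X₅₀ ≤ 9) + Σ P(X₅₀ = k)·P(X₂₁ ≤ 16 - k), summed over k = 10 to 16. This is 0.0591 at p = 32%, 0.0414 at 33%, 0.0284 at 34% and 0.0125 at 36%. If the right benchmark is above 32%, the printed limits are harder to pass by chance. (With 15 as the final limit, the value at 32% is 0.0386. Which whole number applies is a separate question.)

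**Which subjects are affected.** The trial's composite is per subject. Late CPR, vasopressors or ventilation followed by death, bailout or major bleeding already counts. The window matters only for a subject whose sole qualifying event is deterioration after 24 hours. Moving the goal by a quarter of a component rate does not measure that number.

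**Sample size.** N = 71 depends on both 18% and 32%. It is unaffected because both stay as they are.

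**The case for a change.** The strongest case for acting is that the gap may be large. The source study reports 5/32 deteriorations within 24 hours but 15/32 (46.9%) in-hospital deaths, so at least 10 deaths fall outside its 24-hour deterioration count. If the through-discharge deterioration rate were also 46.9%, which is an assumption, the formula would give (28.5 + 30.3 + 46.9 + 11.5)/4 + 10 = 39.3, a goal of 40%. That lies beyond the 36% reached at the upper confidence limit of 5/32, since (28.5 + 30.3 + 32.5 + 11.5)/4 + 10 = 35.7. A 24-hour version of the composite, specified in advance, would be more credible than one devised after a near miss. The planned component rate and the Context Arm description both use the longer window and cannot stand in for it.

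Part of this stands: the mismatch is unacknowledged, its size has no upper bound in the documents, and a near miss would be harder to read. But the example strengthens the point that the goal is strict on this term; it does not expose a risk of a wrong claim.

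The extra analysis would also add little. It can only equal or improve on the primary result, so it could not support success. It would align one term, on the unverified assumption that the source study's 24 hours began at treatment start. It would need onset times from retrospective chart review. Table 3's notes ask for date and time of the treatment decision and initiation but not of deterioration onset. Protocol 6.3 says "Site-reported safety and outcome data will be provided to the CEC for review and adjudication of the following items", and the list that follows has no onset timing; the eCRF itself is not in the documents, so capture cannot be ruled out. Nor would it resolve the larger unknown, which is how the source study defined deterioration.

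**Conclusion.** No change is needed. The windows differ and the documents do not say why, but on window alone the difference cannot favour the device. The goal, the test, the event limits and N = 71 would all stay the same after any proportionate response. The 24-hour label is printed in both documents, and deterioration is reported separately, so a reader of a near miss can see the issue and weigh it. Accepting a possibly strict term is a fair trade-off against a second composite that could not inform the success decision.

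The size is one-quarter weight, or 0.25 points of unrounded goal per point of deterioration rate, with no movement in the rounded goal up to 17.7%. The illustrative goals of 33% to 36% for rates of 20% to 30% are not estimates.

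This rests on equal weighting (inferred from reproducing 21.5%) and on the source study sharing the trial's definition and time zero, which the documents do not give. A broader source definition or an earlier start could offset the effect or reverse it. The conclusion covers the window only. It does not endorse averaging component rates as a benchmark for a composite, or the 10-point margin.

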## 7.3 ANALYTIC DATASETS

The CDISC process would be implemented to generate analytical datasets similar to the Analysis Data Model (ADaM) to be used for tables, lists, and figures (TLFs).

## 7.4 ENDPOINT ANALYSIS

## 7.4.1 PRIMARY ENDPOINT ANALYSIS

The primary endpoint is the in-hospital composite endpoint of all-cause mortality, bailout to an alternative thrombus removal strategy, clinical deterioration, and major bleeding (BARC 3b/3c/5a/5b definition) from the FlowTriever Arm. The rate of the composite endpoint is expected to be 18% and compared with performance goal of 32%:

H0:  $P_S \ge Performance Goal_s versus H_A: P_S < Performance Goal_s$ 

where Ps is the proportion of subjects with in-hospital composite endpoint and Performance Goals is the performance goal of proportion of subjects with in-hospital composite endpoint derived from previous publications and expert opinions on subjects who were non-FlowTriever treatments.

The one-sided binomial's proportion test with normal approximation would be used at a one-sided  $\alpha$  = 0.05. Primary endpoint analysis can be carried out at interim analysis and/or final analysis stage.

## 7.4.2 SECONDARY ENDPOINT ANALYSIS

Secondary Endpoints include both Secondary Safety Endpoints and Utility Measures as listed below:

## Secondary Safety Endpoints

- Frequency of each primary endpoint composite component
- Frequency of Stroke (ischemic or hemorrhagic)
- Frequency of device-related complications
- Access site injury requiring intervention, both venous and arterial

## **Utility Measures**

- Length of hospital stay
- Length of ICU stay
- Use of ECMO, including either pre- or post-treatment initiation and duration
- Time to extubation, if intubated
- Discharge location

Descriptive statistics will be used for secondary endpoints for both the FlowTriever Arm and Context Arm populations. Continuous variable will report min, max, mean, SD, IQR, Q1, Q3 etc. as deemed appropriate. Categorical variable will report frequency counts and percentage. Time-to-event variable may be reported with Kaplan-Meier and/or Cox proportional hazards model estimates.

Additional exploratory analyses on secondary endpoints may include confounder adjustment in generalized linear models (GLMs).

## 7.4.3 INTERIM ANALYSIS

The interim analysis population will be N = 50 enrolled subjects in the FlowTriever Arm with adjudicated in-hospital composite endpoint. Primary endpoint analysis method in **Section 7.4.1** will be used on the interim analysis population to decide whether the study should be stopped early due to achieving early decision rule based on the primary endpoint. The |z - score| threshold is 2.031, which translates to inhospital composite endpoint proportion being  $\leq$  0.186. Therefore, having  $\leq$  9 in-hospital composite endpoint events out of N = 50 may qualify for stopping the study early and conclude achieving significant difference from performance goal = 32% (see Table 9).

Secondary endpoint analysis may be conducted in a descriptive fashion without hypothesis testing, therefore not spending any Type I error ( $\alpha$ ).

## 7.4.4 CONTEXT ARM ANALYSIS

The Context Arm may be analyzed with methods mentioned in primary and secondary endpoint analyses along with descriptive statistics and will not be used to determine study success.

## 7.4.5 PRIOR THERAPY ARM ANALYSIS

Data collection for Prior Therapy Arm subjects will include information surrounding the PE treatment, progression to High-Risk PE, and patient course through hospital discharge. Safety data will also be collected, but not CEC adjudicated or analyzed as outlined for the FlowTriever and Context Arm subjects. Subjects receiving prior advanced treatment for low/intermediate-risk PE in the same hospital setting as a second treatment for high-risk PE likely have a different profile than those receiving advanced care for the first time after diagnosis of high-risk PE, and therefore should be looked at separately. In the spirit of the AHA guidelines for trial design in this patient population, data will be collected to ensure representation of this smaller yet significant group of high-risk PE patients and will be reported in a descriptive manner

## 8 **RISK ANALYSIS**

## 8.1 RISKS TO SUBJECTS

The study involves the use and disclosure of health information. It collects only information relevant to the subject's PE condition and treatment. The information is for research, development, and educational purposes only. It does not specify how the physician will treat PE, and decisions regarding a subject's treatment are not influenced by the study.

Physicians participating in the study are expected to review the indications, contraindications, warnings, precautions, and safety events described in the IFU. As with any endovascular procedure, the treating physician is expected to counsel the subject on the risks and benefits specific to the planned treatment and to obtain the local, procedure-related informed consent per institutional policies and procedures.

## 8.2 MITIGATION OF RISKS

The study was designed to capture real world data regarding the treatment of high-risk PE. The risk of providing this health information is believed to be minimal, as information directly identifying the subject will not be collected in the study database.

## 8.3 STUDY JUSTIFICATION

The FlowTriever System offers an efficient treatment option for high-risk PE patients while obviating the need for thrombolytic drugs and their consequent high bleeding risk including intracranial hemorrhage. Furthermore, FlowTriever may offer quicker relief given the mechanical approach to clot removal versus a pharmacologic approach which can take several hours to have an effect. The current study is designed to assess high-risk PE outcomes in a real-world population that would be encountered in clinical practice.

# 9 ETHICS AND CONFIDENTIALITY

## 9.1 INSTITUTIONAL REVIEW BOARD

This study must be approved by an appropriate IRB representing each investigational site. Securing the approval is the responsibility of the Investigator, as defined by ISO 14155-1 and FDA regulations (21 CFR Part 56), prior to starting the study.

The Sponsor must receive a copy of the IRB approval letter (or equivalent documentation) for the study protocol before the study can be started at that site.

The IRB and Sponsor must approve any significant changes to the protocol, as well as a change of the Principal Investigator. Documentation of IRB approval must be provided to the Sponsor. Records of all study review and approval documents must be maintained by the Investigator in a Regulatory Binder or other appropriate repository and are subject to inspection by the Sponsor or regulatory authority during or after completion of the study.

The Investigator must notify the IRB, as per their reporting guidelines, and the Sponsor when he or she deviates from the protocol. The Sponsor must be notified of all relevant action taken by the IRB and must receive a copy of all study-related correspondence between the Investigator and the IRB.

The IRB must receive notification of the completion of the study and final report after study completion or termination. A copy of these reports must be provided to the Sponsor. The Investigator must maintain an accurate and complete record of all submissions made to the IRB, including a list of all reports and documents submitted.

